### 5.2 Re-estimation of the Sample Size

If after 4,150 patients have been enrolled, less than 530 events have been observed, then power will be reduced. This could happen, for example, if the event rate is lower than expected in the minor stroke cohort. The power is defined by the total number of events, which depends only on the hazard ratio. For a given sample size, a decrease in event rates (overall), assuming a fixed hazard, will decrease power.

The sample size re-estimation should be based solely on the placebo event rate (not the observed difference in treatment groups). The assumed placebo rate is 15.24% with a 95% CI (13.63%, 16.85%) based on a sample of 1907 TIA patients from KPNC. At the time of the first interim analysis when approximately 1/3 of the expected number of events (177) are observed, if the one-sided upper 99% confidence limit around the observed placebo rate does not overlap with those of the assumed rate (Lower 13.63%, Upper 16.85%), then the maximum sample size will be re-estimated based on the observed placebo event rate (given a RRR of 23% as originally assumed).

Figure 2 gives the total sample size needed for a given placebo event rate at various powers. Some scenarios for stopping the trial early versus increasing the sample size are given in section 12.5 as a guide for the DSMB. The DSMB's decision to recommend an increase in the total sample size would take into account the likelihood of success of the trial using the other interim monitoring criteria (see section 12.4 for a flow chart) as well as the safety profile.

### 5.3 Re-estimation of the Sample Size Result

As stipulated in **section 5.2,** following the first interim analysis, the maximum sample size has been re-estimated to be 5,840 subjects.

### 6 DEFINITION OF TARGET POPULATION AND STUDY SAMPLES

### 6.1. Target Population

The target population to which the clopidogrel treatment regimen may be applied are patients 18 years of age or older with high-risk TIA (defined as an ABCD score  $\geq$  4) or minor ischemic stroke (with NIHSS  $\leq$  3) who can be randomized within 12 hours of time last known free from new ischemic symptoms.

### 6.2. Intent-to-Treat Sample

As the primary analysis, all efficacy and safety outcome measures are analyzed under the intent-to-treat (ITT) principle. Under this principle, the evaluable sample includes all randomized subjects, except for re-enrollers. Re-enrollers are patients who are determined to have been enrolled into the POINT trial more than once. For re-enrollers, only the data associated with the first enrollment will be counted in the primary analysis.

### 6.3. Safety Analysis Sample

All randomized subjects are included in the safety analysis sample, regardless of the amount of treatment administered.

### 7 RANDOMIZATION

The randomization will take place centrally via WebDCU™. Subjects will be randomized 1:1 (clopidogrel: placebo), controlling for clinical site using the blocked-urn method.

The detailed randomization scheme and source codes will be provided in the Randomization Plan document. Although a randomization scheme with any constraints would yield some bias in the inferences from using standard analytic methods, Efron (1971) shows the appropriateness of standard statistical tests under the biased coin randomization in large studies. Friedman et al (1998 p. 72) note that the variance terms under the biased coin design tend to be larger than under simple randomization. The consequence is that it would be more difficult to reject the null hypothesis, and therefore, we would be more conservative in determining the significance of the effectiveness of the treatment.

A "Real-Time" randomization procedure is implemented via the WebDCUTM system where the clinical center staff enters the eligibility information of a subject prior to enrollment. If the subject's eligibility status is confirmed, the computer program on the WebDCUTM server will evaluate the treatment arm distribution and generate a study number based on the randomization scheme. The study number will correspond to a specific medication bottle that will be already at the clinical center.

### 8 BLINDING

The study is conducted in a double-blind manner. The placebo for clopidogrel will be identical in appearance and taste. Minor side effects are unusual with the medication, so it is not anticipated that either subjects or clinicians will be able to differentiate the placebo from the active drug. Standard laboratory tests cannot detect the effects of clopidogrel.

### 9 MULTIPLICITY

The primary efficacy hypothesis is tested with the log-rank test for equality of survival curves. This hypothesis is tested with a two-sided 0.05 level of significance.

For secondary outcomes, we will not account for multiplicity. These analyses are merely supportive and exploratory and will be interpreted as such. The overall trial hinges on the primary analysis and interpretation of secondary results is already tempered by their placement. Accounting for multiple testing would also increase the risk that an interesting finding is not subsequently pursued.

### 10 MISSING DATA

Based on the FASTER (Fast Assessment of Stroke and Transient ischemic attack to prevent Early Recurrence) trial, it is anticipated that there would be minimal (2%) loss to follow up for the 90-day assessment of the primary outcome. All efforts should be put forth to ensure near complete follow-up, in particular with the assessment of the primary outcome (time to the composite event of ischemic stroke, myocardial infarction, or ischemic vascular death) and occurrence of death.

Nevertheless, minimal missing data may be inevitable. Since all randomized subjects are included in the primary efficacy outcome analysis, subjects missing outcome data will be censored at the last follow-up assessment time (end of study or last visit preceding loss to follow up). Missing mRS data will be imputed by carrying forward mRS from event visits or by regression imputation.

### 11 MONITORING AND EVALUATION OF CLINICAL CENTER EFFECT

On a semiannual basis, the HR of the treatment effect on outcome measures (efficacy or safety) and its 95% CI are calculated for each clinical center and for all sites combined, and they are graphed in one figure to determine whether any sites are uniquely different from the others or from the overall group. Furthermore, a plot of HRs (y-axis) by number of subjects enrolled at each site (x-axis) is generated. The expectation is that the plot should appear like a funnel where the smaller the number of subjects enrolled, the greater the variability. This graph also assists us in determining where, if any, outliers are with respect to the sites. If any outliers are detected, further investigation into the reasons is made to ensure that the trial conduct at those sites is in accordance with the protocol and GCP Guidelines. These figures and graphs are included in the closed DSMB reports.

Inclusion of clinical center effect in the efficacy analysis is discussed in Section 12.1.4 below.

### 12 EFFICACY ANALYSIS

### 12.1. Primary Outcome Variable Analysis

### 12.1.1. Primary Outcome

The primary efficacy outcome measure is the composite event of ischemic stroke, myocardial infarction, or ischemic vascular death within 90 days. These events will be adjudicated by the Adjudications Committee.

### 12.1.2. Statistical Hypothesis

The set of statistical hypotheses can be stated in terms of hazard functions as:

$$H_0$$
:  $h_c(t) = h_p(t)$  versus  $H_A$ :  $h_c(t) \neq h_p(t)$ 

where  $h_c(t)$  and  $h_p(t)$  are the hazard rates for the clopidogrel and placebo groups, respectively. The minimum effect size of clinical interest is a relative hazard rate reduction of 25%, or relative risk reduction of 23%. The hazard rate for the placebo group is assumed to be 16.5%.

### 12.1.3. Primary Efficacy Analysis (ITT)

The primary efficacy null hypothesis of the equality of survival curves is tested with the log-rank test. The overall Type I error for the primary analysis will consider two-sided alpha=0.05 significant.

The primary analysis will be intention to treat, with inclusion and treatment group defined at the randomization assignment. Missing values will remain missing and patients will be censored at their last follow-up assessment; based on projected loss rates, it is expected that only 5 subjects will be lost at 7 days and 70 subjects lost at 90 days, so the problem is relatively minor. Kaplan-Meier estimates of the cumulative risk of an event during maximum 90-day follow-up will be reported, with HRs and 95% CI calculated using Cox proportional hazards methods (to provide an estimate of treatment effect) and the log-rank test to evaluate the treatment effect. This approach is being taken to maximize the time dependent information in the trial while still acknowledging the ease of interpretation of risks. For the Cox proportional hazards method, the Efron method will be used when there are ties since this method closely approximates the exact method, but requires less computing resources.

The primary outcome is composite of ischemic stroke, MI, or ischemic vascular death occurring up to 90 days. However, the 90 day visit may occur within +-14 days of the target visit. For patients with an event, the time to event will be the days from randomization to the first adjudicated primary outcome event (if it occurred before 90 days). Events occurring after 90 days (e.g. day 91) will not be counted in the primary analysis. Patients for whom there was no event and whose follow-up visit occurred after day 90 will be censored at exactly 90 days. For patients without a 90 day visit, the censoring date will be determined by the last collected QVSFS (censoring time will be the actual days from randomization). The Kaplan Meier curves will use the actual days up to day 90. For this figure, the "# at risk" will be reported at baseline, 7 days, and 90 days.

Likewise, the ITT analysis will be repeated for the primary and secondary efficacy and safety outcomes.

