8.5.3 Procedure for Expedited Reporting of SAEs/Clinical Outcomes

Clinical outcomes may be discovered during the 7-day telephone follow-up, the 30-day phone contact, the 90-day follow-up appointment, or at any point during the study period. For subjects considered lost to follow-up, efforts should be made for up to 150 days from randomization to determine if an outcome event occurred during the subject's 90 days in the study. When a clinical outcome is discovered, the Site PI is responsible for submitting it **within 5 days (within 24 hours for sites in the UK) of the discovery of the event** on the online SAE/Clinical Outcome case report form.

The Hub PI (for NINDS NETT-CCC Network sites) or Site PI (for POINT Clinical Research Collaboration (CRC) sites) are responsible for the monitoring, follow-up and appropriate documentation of all clinical outcomes until resolution or the end of study for the subject. The Site/Hub PI will work with the appropriate Site Manager to prepare an Event Packet for outcome events, including copies of discharge summaries, neurology, cardiology or other consultation notes, head imaging reports, appropriate laboratory values, and a narrative summary, plus any supplemental documentation based upon adjudication category assigned to the event, with all unique identifiers removed.

When the SAE/Clinical Outcome CRF is submitted for a fatal SAE or a clinical outcome, the appropriate Site Manager is then responsible for reviewing the information for completeness. If the information is deemed insufficient, the Site Manager will request additional information from the site.

The Site Manager will work with the Site/Hub PI to prepare an Event Packet, as described above. When the SAE/Clinical Outcome information is deemed sufficient by the Site Manager, the Clinician Event Coordinator (CEC) is charged with performing the Clinical Outcome Review (COR). The COR includes review of both Clinical Outcomes and SAEs.

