9.4 Follow-up

9.4.1 Follow-up 7 Day Phone Call

The Site Coordinator will contact subjects by telephone (or in person) at 7 days. A review of SAEs/Clinical Outcomes, concomitant medications and compliance with study medication will be assessed. The QVSFS, a screen for stroke-free status questionnaire [155] will also be administered. If subject contact suggests that a possible stroke, TIA or myocardial infarction may have occurred, an Outcome Event Visit will be scheduled.

9.4.1.1 30 Day Phone Contact

The Site Coordinator will contact subjects by telephone at 30 days to uncover any issues or concerns that might impact study drug compliance and retention in the study.

While no study data will be collected for the 30-day phone contact, if subject contact suggests that a possible stroke, TIA or myocardial infarction may have occurred, an Outcome Event Visit will be scheduled.

9.4.2 90 Day In-Person or Phone Follow-up

A review of SAEs/Clinical Outcomes, concomitant medications and compliance with study medication (via the Morisky questionnaire) will be assessed. The QVSFS, mRS and NIHSS will also be administered.

At the 90 Day visit, the study physician will discuss options for antiplatelet therapy. Unless the subject's treating neurologist or primary care physician has a particular preference for one of the proven antiplatelet medications, clopidogrel 75 mg will be prescribed for subjects who can afford clopidogrel or have medical coverage for it. For others, aspirin 75-100 mg will be prescribed, consistent with American Stroke Association guidelines. The physician will confirm that a high-dose, high-potency statin is also prescribed [158] and that blood pressure and diabetes are well controlled. Diet, exercise, and appropriate action in the event of stroke will also be discussed.

The 90 Day follow-up should be completed during an in-person visit whenever possible; under limited circumstances, for example, if the subject is unable to come in for follow-up, the visit may be completed by telephone. CRF completion for the visit will be guided by whether the visit was conducted by phone or in person. For visits completed over the phone, the omission of the NIHSS assessment will not result in a protocol deviation. The 90-day assessment does not have to be completed by the PI. It can be completed by anyone on the study team that has completed the appropriate POINT study training and whose certifications are current.

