9.4.2.1 Subjects Considered Lost To Follow-up

A subject is considered to be lost to follow-up (LTFU) when continued contact with the subject cannot be maintained and, despite an active follow-up effort, the site is unable to collect reliable information about the outcome event status of the subject up to 150 days following randomization (the 90 day enrollment period, and up to 60 days after the projected end of the subject's enrollment).

Information about outcome events that occurred during the subject's 90 day enrollment will be considered *reliable* when Form 14: Questionnaire for Verifying Stroke Free Status and/or Form 19: SAE/Clinical Outcome Reporting are completed based on contact with the subject, or the subject's caregiver or alternate contact. Events reported in this way will be adjudicated and included in the primary analysis.

A subject can be considered lost to follow-up when the clinical site can show documented attempts to reach the subject, and the period beyond the final scheduled study visit has reached 60 days (i.e., 150 days after randomization). For any subject who may be lost to follow-up, the POINT Clinical Site must discuss the subject with the appropriate NETT or CRC Study Manager and the UCSF Clinical Coordinating Center team before assigning that subject lost.

POINT Clinical Sites will need to demonstrate and document in WebDCU (Form 17 - End of Study: General Comments field) at least three (3) attempted telephone contacts by research personnel. A progress note, including the time and date of each attempt, should be added to the participant's study file for each contact. After attempts at phone contact are considered unsuccessful, or a subject has been reached but fails to appear for the 90 day visit, research personnel at sites must also generate and send at least one (1) letter using institutional letterhead and envelope. The letter should be sent

using Certified Mail™ with Return Receipt Service (or equivalent in other countries) for evidence of delivery to the participant's address, allowing a week for the subject to respond to the site. The receipt should be added to the participant's file, and a progress note, along with a copy of the letter(s), should also be placed in the subject's study file. When subjects cannot be contacted despite the site team implementing these approaches, investigators should attempt to determine the subject's vital status at 90 days (i.e., living or deceased) using locally-approved resources.

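### SAP 12.1.3 credits event-free time only to the last stroke questionnaire when the day-90 visit is missing, yet counts later events from any source; other sections give other censoring dates

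*SAP*

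**What the plan says.** **Events.** Under SAP 12.1.3, "the time to event will be the days from randomization to the first adjudicated primary outcome event", provided it falls within 90 days; no day-90 visit is required. Protocol 8.5.3 says of subjects considered lost that "efforts should be made for up to 150 days from randomization to determine if an outcome event occurred". Protocol 9.4.2.1 treats late information as reliable when "Questionnaire for Verifying Stroke Free Status and/or Form 19: SAE/Clinical Outcome Reporting are completed based on contact with the subject", or with a caregiver or alternate contact, and adds: "Events reported in this way will be adjudicated and included in the primary analysis". Under Protocol 4.6.1, a death that cannot readily be put down to a non-ischemic cause is an ischemic vascular death, and so a primary event.

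**Event-free time.** SAP 12.1.3: "For patients without a 90 day visit, the censoring date will be determined by the last collected QVSFS". The Schedule of Activities (Protocol 1.2) places this questionnaire at day 7, at day 30 in parentheses, at day 90 and at event visits. On day 30, Protocol 9.4.1.1 says: "While no study data will be collected for the 30-day phone contact". Event visits follow ischemic stroke, TIA or myocardial infarction (Protocol 9.4.3).

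**Other outcomes.** SAP 12.1.3 ends: "Likewise, the ITT analysis will be repeated for the primary and secondary efficacy and safety outcomes". SAP 12.5.1 lists all-cause death and the hemorrhage outcomes among these. For subjects who cannot be reached, Protocol 9.4.2.1 asks sites to try to establish "vital status at 90 days (i.e., living or deceased) using locally-approved resources".

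**Other censoring wording.** Protocol 10.2.1, SAP 10 and an earlier sentence of SAP 12.1.3 itself censor at the last follow-up assessment; the first two explain this as study end or the last visit before loss. Protocol 9.4.2.2 puts study exit at death for a subject who dies before the day-90 window, and at day 150 for a subject lost to follow-up.

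**The concern.** Events and event-free time are held to different standards of evidence. An event after the last questionnaire enters the analysis from any source, while freedom from an event after that date usually does not. Among patients without a day-90 visit, those with a later event then stay in the risk set and those without one leave it. Censoring that depends on the outcome in this way violates the Kaplan-Meier assumption and pushes the estimated risk up.

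Two cases show the mismatch:
- A patient dies of hemorrhage on day 60 with no event visit. For the primary outcome the patient is censored near day 7, although followed to death.
- A patient is confirmed alive at day 90 by a vital-status search. Applied literally to all-cause death, the rule still censors near day 7, whereas a death found by the same search counts.

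Because the passages disagree, one patient could be censored at about day 7, at death or at day 90, depending on which sentence the programmer follows. The 90-day Kaplan-Meier risks are reported results, so the choice should be settled before unblinding.

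**Working it through.** **1. The plan's own measure of the problem.** SAP 12.1.3 expects 5 subjects lost at 7 days and 70 at 90 days. SAP 5.1 gives 2% loss, N = 4,150, placebo risk 0.1524 and HR 0.75.
- Clopidogrel risk: 1 − (1 − 0.1524)^0.75 = 0.1166. Mean risk: (0.1524 + 0.1166)/2 = 0.1345.
- Lost at 90 days: 0.02 × 4,150 = 83. Among event-free subjects: 83 × (1 − 0.1345) = 71.8, against 70 stated.
- Lost by day 7 if losses are uniform: 83 × 7/90 = 6.5, against 5 stated.

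Both agree to within two patients, so 2% is the planning figure. The 70 belongs to N = 4,150; at the re-estimated 5,840 the same arithmetic gives 0.02 × 5,840 × (1 − 0.1345) = 101.

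**2. Model of the rule.** Let *p* be the true 90-day risk, *f* the share of events by day 7, and *q* the share of patients with no day-90 visit, independent of outcome. Assume every later event in these patients is captured, and every event-free one is censored at day 7:

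estimated risk = 1 − S₇ × [1 − p(1 − f) / (S₇ − q(1 − p))], with S₇ = 1 − p·f.

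*Event timing.* The emergency-department cohort in Protocol 2.6 had 50% of events by day 5 and 73% by one month. Interpolating on log time: 50% + 23% × ln(7/5)/ln(30/5) ≈ 54% by day 7 (an assumption).

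*Placebo, q = 2%.* S₇ = 1 − 0.1524 × 0.54 = 0.9177. Later events = 0.1524 × 0.46 = 0.0701. At risk after day 7 = 0.9177 − 0.02 × 0.8476 = 0.9008. Estimated risk = 1 − 0.9177 × (1 − 0.0701/0.9008) = 0.1537, an excess of 0.13 points.

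| No day-90 visit (q) | Placebo risk, f = 54% | Excess (points) | Excess, exponential timing (f = 8.4%) |
|---|---|---|---|
| 2% (planned loss) | 15.37% | 0.13 | 0.24 |
| 5% (assumed) | 15.58% | 0.34 | 0.63 |
| 8% (assumed) | 15.80% | 0.56 | 1.03 |

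Taking f = 50% gives 0.14 points at 2%. Moving the censoring point to day 30 (f = 73%) gives 0.08. If none of the later events are captured, the excess is zero at every q.

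**3. Hazard ratio** (ratio of log survival at day 90).
- Equal loss of 2%: clopidogrel risk goes from 11.66% to 11.77% and the HR stays 0.750.
- Placebo 1%, clopidogrel 3%: ln(1 − 0.1182)/ln(1 − 0.1531) = 0.757.
- Placebo 3%, clopidogrel 1%: ln(1 − 0.1171)/ln(1 − 0.1544) = 0.743.
- No true effect, with 1% against 3%: 1.01 or 0.99.

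**4. All-cause death.** Take the 3% in SAP 13.2 and, as an assumption, deaths spread evenly over 90 days (f = 7/90 = 0.078). At q = 2%: S₇ = 0.9977, later deaths = 0.0277, at risk = 0.9977 − 0.02 × 0.97 = 0.9783, estimated risk = 3.05%, a relative excess of 1.8%. At 5% and 8% it is 4.7% and 7.8%. If deaths come early, as in the cohort timing above, it is about half as large.

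**The case against.** Much of the gap may be closed in practice. Form 14 is itself the QVSFS, and Protocol 9.4.2.1 accepts it from the subject, a caregiver or an alternate contact up to day 150, so event-free time confirmed that way is kept. The day-90 visit may be done by telephone, and event visits also record the questionnaire. The SAP expects about 70 losses and regards the problem as relatively minor. SAP 13.2 separately reports deaths within 90 (±14) days as proportions, which this censoring does not touch. The closing sentence of SAP 12.1.3 need not carry a stroke questionnaire's date into a mortality analysis.

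All of this limits the size, and some stronger inferences fail because of it:
- A reader might infer that censoring at day 7 will be common. The documents give no frequency; it happens only where no late or event-visit questionnaire exists.
- A reader might infer that every 90-day risk is biased upward. That requires later events to be captured selectively. With no capture and independent loss the bias is zero, and if unreached patients had more events the risk would be understated.
- A reader might infer that confirmed survival should extend primary-outcome follow-up. Being alive at day 90 does not show freedom from stroke or myocardial infarction; the argument holds only for all-cause death.
- A reader might infer that the primary test is compromised. With equal loss it is not.

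What stands is the asymmetry in the written rule, its poor fit to death and bleeding outcomes, and the conflict between passages. The rule also covers every patient without a day-90 visit, including withdrawals and non-ischemic deaths (Protocol 9.4.2.2), so the affected group can exceed the projected losses.

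**Conclusion.** The rule is wrong as written, but its likely effect is small. At the planned 2% the overstatement of the 15.24% placebo risk is at most about 0.13 points under the cohort's event timing, or 0.24 under exponential timing. It reaches about 0.34 and 0.56 points (0.63 and 1.03 exponential) only at assumed missed-visit rates of 5% and 8%. These figures assume loss independent of outcome, full capture of later events and no late questionnaire, so they are upper figures for each rate and timing. The HR is essentially unchanged unless loss differs by arm, and 1% against 3% moves it only to 0.743 or 0.757. The primary log-rank conclusion is not threatened. The case for changing the text rests on the conflicting rules and on the discarded follow-up, most clearly for all-cause death.

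**What to change.** Reconcile Protocol 10.2.1, SAP 10 and SAP 12.1.3 into one rule, stated per outcome:

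1. Subjects without the outcome are censored at the earliest of day 90, the date of death from a cause that is not the outcome, and the last date on which freedom from that outcome is documented in data already collected (Form 14, event visit, Form 19, alternate contact).
2. For all-cause death, use the last date known alive, including the 90-day vital status.
3. Add a sensitivity analysis that applies the same ascertainment cut-off to events and to censoring in patients without a day-90 visit. It is needed because rule 1 narrows the asymmetry without removing it: patients who fall silent are still censored early while their later events count.

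The cost is SAP wording, aligned wording in Protocol 10.2.1, a small programming change and one extra analysis, settled before unblinding. No new day-30 data collection is needed. That would change a contact defined as collecting no study data and would go to ethics review across up to 350 sites, for little gain: even censoring at day 30 leaves 0.08 of the 0.13 points at 2%.
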